9.6 Reporting of Serious Adverse Events

All Serious Adverse Reactions and Unexpected Serious/Adverse Reactions must be reported to the Coordinator within 24 hours (one working day) of the Investigator becoming aware of them. Preference is given to the SAE report via e-mail at [contact].

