9.1 Adverse Events (AE)

Any adverse medical event in a patient or clinical trial subject who has received a pharmaceutical product that does not necessarily have a causal relationship with this treatment is referred to as a Serious/Adverse Event (S/AE). Any undesirable and unanticipated sign (including an abnormal laboratory finding), symptom, or disease that is temporally connected with the use of an Investigational Product, whether related or not, is referred to as an adverse event (AE).

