9.2. Adverse Drug Reaction (ADR)

All unanticipated and undesirable reactions to an Investigational Product caused by any application or dose given. The phrase "responses to an Investigational Product" refers to a causal relationship that has been determined by either the Investigator or the Coordinator. Reasonable implies that there is a hint or argument that a causal relationship exists. In the case of commercialized Investigational Products, an unpleasant and unanticipated reaction to a product happens in applications that are often utilized in man for disease prevention, diagnosis, or therapy, or to affect physiological function.

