9.2.1 Serious Adverse Event or Serious Adverse Reaction (SAE/SAR)

Protocol Number: FSNANO08032022 -2.0 amendment 1 Date: 20032023	
STUDY Code: N-HANCE	Page 14 of 26

Serious Adverse Events will be considered for AE documentation due to the patient's underlying constitution. Serious Adverse Drug Reactions will be handled as outlined below.

Expedited Reporting is required if the following criteria apply (ICH E2A):

1. Serious
2. Unexpected
3. A reasonable causal relationship to study treatment.

An Adverse Drug Reaction is considered serious if it:

- Results in Death
- Is life-threatening
- Requires additional inpatient hospitalization or prolongation of existing Hospitalization
- Results in persistent or significant disability/incapacity
- Results in a congenital anomaly or birth defect
- Other medically significant events that require immediate medical or surgical Intervention

Unexpected means:

- Not consistent with Investigators Brochure or SmPC

Causal Relationship means:

- There are facts/evidence to suggest a causal relationship
- As judged by the reporting health care professional to have a reasonable suspected causal relationship

NOTE

Death: is the result of an Adverse Event The medical condition that caused death, such as an underlying disease or an accident, must be reported in detail

Life-threatening: in the definition of a Serious Adverse Event or Adverse Reaction refers to an event in which the patient was at risk of death at the time of the event; it does not refer to an event which hypothetically might have caused death if it was more severe

In some circumstances, medical judgment should be utilized to determine the seriousness of an Adverse Event / Reaction. Important Adverse Events / Reactions that are not immediately life-threatening or do not result in death or hospitalization but may put the patient at risk or demand intervention to avoid one of the other outcomes specified in the description above may also be deemed serious.

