9.5.2 Definition of Adverse Event causality

The following criteria are used to indicate the degree of causation (all points should be reasonably complied with) based on the WHO-UMC system for standardized case causality assessment (www.who-umc.org):

Definite

- Event or laboratory test abnormality, with plausible time relationship to drug intake
- Cannot be explained by disease or other drugs
- Response to withdrawal plausible (pharmacologically, pathologically)
- Event definitive pharmacologically or phenomenologically (i.e. an objective and specific medical disorder or a recognized pharmacological phenomenon)
- Re-challenge satisfactory, if necessary

Protocol Number: FSNANO08032022 -2.0 amendment 1 Date: 20032023	
STUDY Code: N-HANCE	Page 16 of 26

Probable

- Event or laboratory test abnormality, with reasonable time relationship to drug intake
- Unlikely to be attributed to disease or other drugs
- Response to withdrawal clinically reasonable (for details refer to WHO-UMC)
- Re-challenge not required

Possible

- Event or laboratory test abnormality, with reasonable time relationship to drug intake
- Could also be explained by disease or other drugs
- Information on drug withdrawal may be lacking or unclear

Unlikely

- Event or laboratory test abnormality, with a time to drug intake that makes a relationship improbable (but not impossible)
- Disease or other drugs provide plausible explanations

Not related

The event does not follow a reasonable temporal sequence from the administration of the IMP and is clearly related to other factors, such as clinical state, therapeutic intervention or concomitant therapy.

Not assessable

- Report suggesting an adverse reaction
- Cannot be judged because the information is insufficient or contradictory
- Data cannot be supplemented or verified

All cases judged by any or both assessors as having a “reasonable causal relationship” to the IMP qualify as ADR. This corresponds to the categories “definite”, “probable” and “possible”.

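### Section 9.6 applies its 24-hour duty only to events already classed as reactions, so other serious events have no prompt route to the Coordinator's causality judgement; its two time limits also differ

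*Protocol*

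**What the plan says.** Section 9.6 has a heading wide enough for every serious event, "9.6 Reporting of Serious Adverse Events", and it calls the form an SAE report. The duty itself is narrower: "All Serious Adverse Reactions and Unexpected Serious/Adverse Reactions must be reported to the Coordinator within 24 hours (one working day", with the clock running from the investigator's awareness.

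Other parts of section 9 bear on this:

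- Section 9.2 explains that a response to the product "refers to a causal relationship that has been determined by either the Investigator or the Coordinator".
- Section 9.5.2 counts as adverse drug reactions "All cases judged by any or both assessors as having a" reasonable causal relationship to the product. Ratings of definite, probable and possible qualify. Unlikely, not related and not assessable do not.
- Section 9.2.1 says that "Serious Adverse Events will be considered for AE documentation". For expedited reporting it refers to the causality judgement of the professional who reports.
- Section 9.5 requires every adverse event, serious or not, to be recorded in the CRF with its relationship to treatment, and to be reported. It gives no recipient and no deadline.
- Section 9.7 declares no exemption from expedited reporting.

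**The concern.** The protocol sets up two causality assessors, and a positive judgement by either one is enough. That protects against a single wrong call only if the second assessor sees the events the first has dismissed, and sees them in time. Section 9.6 makes the prompt report depend on the first assessor's answer. If the investigator wrongly dismisses a serious event as unrelated, nothing in the protocol brings it to the Coordinator while expedited reporting is still timely.

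The time limit has its own fault. It is given in two forms that are treated as equal but differ over weekends and holidays, so a site could take either as the rule.

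**Working it through.** The point rests on no sample size, power or alpha. The check sets the sections side by side and then computes elapsed hours for the time limit.

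**Step 1: what triggers the duty.** Section 9.6 names serious adverse reactions and unexpected serious/adverse reactions. The slash may bring in non-serious unexpected reactions, but these are still reactions. Applying the section 9.5.2 scale to the investigator's rating of a serious event gives:

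| Investigator's rating | Reaction on that rating? | Within the 9.6 duty? | Could the Coordinator's judgement change the status? |
|---|---|---|---|
| Definite, probable, possible | Yes | Yes | No, one positive judgement suffices |
| Unlikely, not related, not assessable | No | No | Yes |

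The last two columns run in opposite directions. For classification as a reaction, the second judgement is redundant for the events that section 9.6 sends promptly, and decisive only for those it does not send. The not assessable category is the sharpest case, because section 9.5.2 describes it as a report that does suggest a reaction but whose information is insufficient or contradictory.

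**Step 2: who the assessors are.** Section 9.5.2 does not name them. That they are the investigator and the Coordinator is inferred from section 9.2.

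**Step 3: other routes to the Coordinator.**

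- Section 9.5 (CRF record of all adverse events): no recipient, no deadline.
- Section 13.3 (direct access) and section 14.2 (monitoring visits): intervals set by the project's needs.
- Section 15.7.1 (CRF completion): asks for timely data without a figure. Its only dated requirement, signed CRFs ready for the monitor, falls within two weeks of the end of the study.
- Section 16 (all data to the Coordinator): no deadline.

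These routes exist. None has a deadline suited to expedited reporting, and none provides for a second causality review.

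**Step 4: the two clocks.** The limit reads "within 24 hours (one working day) of the Investigator becoming aware of them". The protocol does not define a working day, so a Monday-to-Friday week is assumed here.

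| Investigator aware | 24 hours ends | One working day ends | Elapsed on second reading |
|---|---|---|---|
| Monday to Thursday, no holiday | Next day, same time | Next day, same time | about 24 h |
| Friday 17:00 | Saturday 17:00 | Monday 17:00 | 3 × 24 = 72 h |
| Friday 17:00, Monday a holiday | Saturday 17:00 | Tuesday 17:00 | 4 × 24 = 96 h |

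The gap is 72 − 24 = 48 hours over an ordinary weekend and 96 − 24 = 72 hours over the long one. The two limits agree only when the next calendar day is a working day.

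**The case against.** The strongest reply is that section 9.6 is loosely worded rather than restrictive. Its heading and its reference to an SAE report suggest that all serious events were meant. This is plausible, but the operative sentence names reactions only, and section 9.2.1 separately sends serious events to adverse event documentation. A site following the text would report reactions only.

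A second reply is that no prompt second assessment is promised. The rule in 9.5.2 sets no timing, and for expedited reporting 9.2.1 looks to the reporting professional, so 9.2.1 and 9.6 agree with each other. That is fair as far as it goes. But 9.2 and 9.5.2 then give the Coordinator a power that can be used only late, in a protocol that declares no exemption from expedited reporting.

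Some stronger readings are tempting but not supported:

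- A reader might infer that the Coordinator never sees the other serious events. Sections 9.5, 13.3 and 16 give later access, so the gap is one of promptness and of a defined step.
- A reader might infer from "Any undesirable and unanticipated sign" in section 9.1 that anticipated adverse events are lost to the safety analysis. The first sentence of 9.1 has no such limit, and 9.5 requires all adverse signs and symptoms to be recorded. The real clash is smaller: section 9.2 confines adverse drug reactions to unanticipated ones, while section 9.3 defines expected ones.
- A reader might infer that the reported count of serious reactions will rest on one assessor. The protocol describes no such tabulation, and nothing stops the Coordinator from reclassifying events from CRF data before analysis.

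**Conclusion.** The point stands as a fault in a stated rule. The prompt report to the Coordinator depends on the investigator's own causality rating, so the either-assessor rule in 9.2 and 9.5.2 cannot work in time for the serious events where it could matter. This rests on the inference from 9.2 about who the assessors are.

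The number of events affected cannot be given. The protocol states no expected number of serious events, and to say that all events rated unrelated fall outside 9.6 only restates the rule.

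The time limit is inconsistent as written: 24 hours on one reading, and about 72 hours from a Friday (96 with a Monday holiday) on the other, given a Monday-to-Friday week. On other days the two roughly agree.

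The consequence is for safety oversight. The primary comparison, sample size, power and alpha are unaffected.

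**What to change.** 1. In section 9.6, require all serious adverse events, whatever the investigator's causality rating, to be reported to the Coordinator within 24 hours of the investigator's awareness. Delete the bracketed "one working day" so that one limit remains.
2. In section 9.2.1, say that serious adverse events are reported under 9.6 as well as documented, and reconcile its causality wording for expedited reporting with 9.2 and 9.5.2, so that it is clear whether a positive judgement by either assessor is enough.
3. In section 9.5.2, name the two assessors.
4. As a minor wording point, reconcile the word unanticipated in the section 9.2 definition with the expected reactions of 9.3, for example by using unintended.

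The cost is a wording amendment with the ethics review that section 15.4 requires, and some extra SAE forms. These should be few in healthy adults observed for 180 days, although the protocol gives no figure to confirm that.

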9.7 Exemption from expedited reporting

Not applicable.

9.8 Adverse Event/Reaction follow-up procedure

Adverse Events/ Reactions will be followed up throughout the course of the clinical study and any changes will be recorded in the CRF.

10. STUDY SCHEDULE

10.1 Procedures at Each Visit

Visit 1 - Screening - Study day 0

- Demographic data
- Medical history and risk factors
- ICF
- Randomization
- Primary and secondary outcomes

Visit 2 - Efficacy Evaluation -Study day 30

- Primary Outcomes
- Secondary Outcome

Visit 3 - Efficacy Evaluation -Study Day 90

- Primary Outcomes
- Secondary Outcome

Visit 4 - Efficacy Evaluation - Study Day 180

- Primary Outcomes
- Secondary Outcome

10.2 Assessment of Compliance

Compliance will be documented in the CRF by recording the date and time of administration. The number of IV infusions actually given to each patient will be calculated as a percentage of the total number of IV infusions planned per protocol, providing a measure of treatment adherence.

10.3 Risk assessment and Precautionary Measures

The investigational medicinal product is in clinical use for many years and has demonstrated a very benign safety profile.

The safety information for the IMP is provided in the SmPC in Appendix 1.

11. STUDY AND TREATMENT DURATION

Study/Treatment start: 10/2022

Study/Treatment end: 11/2024

12. STATISTICAL METHODS

The final statistical analysis of the study will be performed by a qualified biometrician and will fulfill all ICH/GCP requirements for handling clinical study data. The statistical analysis, including any subgroup analysis will be agreed upon prior to data evaluation and the results will be fixed in a statistical analysis plan (SAP) which will be established prior to unblinding of the data. The study data will be analyzed and

Protocol Number: FSNANO08032022 -2.0 amendment 1 Date: 20032023	
STUDY Code: N-HANCE	Page 18 of 26

the Statistical Report written as soon as all study data are entered into the study database and the entered data are validated.

The analysis will be based on pre-specification of the primary analyses and control of multiple level alpha. The power for this study is determined based on the following design specifications:

- K=2 experimental treatments will be included in the trial.
- A significance level of $\alpha=0.05$ will be used, in combination with Dunnett's correction.
- The standard deviations of the responses will be assumed to be: $(\sigma_0, \dots, \sigma_K)=(1, 1, 1)$.
- The minimum marginal power will be controlled to level $1-\beta=0.9$ under each of their respective least favourable configurations.
- The interesting and uninteresting treatment effects will be: $\delta_1=0.5$ and $\delta_0=0$ respectively.
- The target allocation to each of the experimental arms will be: the same as the control arm.
- Therefore, the realised allocation ratios to the experimental arms are: $(r_1, \dots, r_K)=(1, 1)$.
- The maximum familywise error-rate is: 0.05.
- The minimum marginal power is: 0.9.
- The following critical threshold should be used with the chosen multiple comparison correction: 0.028.
- 10% adjustment for dropouts
- The total required sample size is: $N=270$. The required sample size in each arm is: $(n_0, \dots, n_K)=(90, 90, 90)$.

Source: Grayling MJ, Wason JMS (2020) A web application for the design of multi-arm clinical trials. *BMC Cancer* 20:80. DOI: 10.1186/s12885-020-6525-0

It is the primary endpoint of this study to assess the efficacy of N-PEP-12 on the Test of Attentional Performance outcomes in healthy middle-aged and older adults at 90 and 180 days after baseline.

Missing data

Missing data of the type 'missing completely at random' (MCAR), which in principle will not bias the results; the analysis procedure should be able to cope with partially missing data of such a type. In many studies this type of data is treated by LOCF replacement (Last Observation Carried Forward) as far as there exist follow-up measurements at previous visits.

In a study like the one planned there might also be informatively missing data (missing not at random, MNAR): participants of the study died or are unable to complete the tests because of brain-related impairment. Neglecting these missing data might introduce bias.

In order to identify each type of missing data, outcome scales will be coded for every patient and visit according to the following scheme:

- 1 = valid (complete task)
- 2 = unable to complete (TBI-related neurological reason) [describe reason]
- 3 = not completed (different reasons, not TBI related) [describe reason].

For outcome scales with code "2" a worst rank imputation will be introduced for the corresponding patients since these data are informatively missing (missing not at random, MNAR). These missing data are replaced by the worst possible score of the corresponding outcome scale.

For outcome scales with code "3" a LPCF replacement will be introduced (Last Percentile Carried Forward) as far as previous follow-up evaluations exist. This method carries forward the actual status information of

Protocol Number: FSNANO08032022 -2.0 amendment 1 Date: 20032023	
STUDY Code: N-HANCE	Page 19 of 26

the patient population, using the percentile value with back transformation to raw scale, instead of the last value carried forward. This approach was recently developed and recommended by O’Brien, Zhang and Bailey (2005) for the analysis of data from chronic, progressive diseases such as dementia. According to their simulation study the calculated estimators should be negligibly biased by missing data. If no general change of patients over time occurs the method is more or less identical with LOCF (Last Value Carried Forward), if change occurs bias is minimized. If no previous follow-up measurement exists, the outcome scale remains missing.

Study populations and protocol violations

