3.1.1 Primary Variables

Test of Attentional Performance (TAP) subtests:

- Alertness
- Working Memory
- Divided Attention

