8.1.1.1 Alertness Subtest

For the Alertness (phasic alertness) subtest, the reaction time is tested under two conditions. The first

Protocol Number: FSNANO08032022 -2.0 amendment 1 Date: 20032023	
STUDY Code: N-HANCE	Page 12 of 26

condition involves simple reaction time measurements in which a cross appears on the monitor at irregular points and the subject must respond as quickly as possible by pressing a key (Zimmerman & Fimm, 2022).

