8.1.1.3 Divided Attention Subtest

A visual and an auditory task must be completed concurrently in this test. The tasks focus on attentional selectivity, focused attention and visuo-spatial attention (Zimmerman & Fimm, 2022).

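### The stated familywise error of 0.05, threshold of 0.028 and power of 0.9 are derived for two doses on one response, but the protocol names three primary TAP subtests and no rule for combining them

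*Protocol*

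**What the plan says.** Section 12 (repeated in the synopsis) lists the design inputs: "K=2 experimental treatments will be included in the trial", alpha 0.05 with Dunnett's correction, a standard deviation of 1 in each arm, one effect of 0.5 against 0, equal allocation, marginal power 0.9 and a 10% dropout allowance. From these it reports "The maximum familywise error-rate is: 0.05" and "The following critical threshold should be used with the chosen multiple comparison correction: 0.028", with 90 participants per arm and 270 in total. It does not say whether tests are one-sided or two-sided.

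Section 3.1.1 gives the primary variables as "Test of Attentional Performance (TAP) subtests" and lists Alertness, Working Memory and Divided Attention. The ITT definition and the baseline comparison in Section 12 also refer to primary efficacy criteria in the plural. Section 12 promises control of the multiple-level alpha, but the only correction it specifies is Dunnett's, which works across doses.

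Section 8 describes the tasks without naming a score. For Alertness, "the reaction time is tested under two conditions"; for Divided Attention, "A visual and an auditory task must be completed concurrently in this test". The synopsis narrows two of the subtests, to phasic alertness and to difficulty level 3 of Working Memory.

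**The concern.** Dunnett's procedure protects against testing two doses against a shared placebo. It makes no allowance for testing several outcomes. With one score per subtest, three subtests and two doses give six primary tests at Day 90, while the error rate and power were worked out for two.

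The 0.05 and 0.9 will be read as properties of the trial's primary conclusion. As written, they belong to one response that the protocol does not identify. A later analysis that simply follows 0.028 on each subtest, and claims on any success, would carry a false-positive risk well above the declared maximum. An analysis that demands success on all three would be much less likely to reach a positive conclusion than a reader of the 0.9 would expect.

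**Working it through.** **Inputs from Section 12:** K = 2, alpha 0.05, Dunnett, SD 1, effect 0.5, power 0.9, 1:1:1 allocation, 10% dropout. Equal allocation with a shared placebo gives correlation 0.5 between the two dose statistics. **From Section 3.1.1:** three subtests. **Assumed, because the protocol gives none:** a common correlation r between subtests.

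**1. Reproducing the plan's figures (one response).**
- One-sided Dunnett: solve P(max(Z1, Z2) > c) = 0.05 with correlation 0.5. This gives c = 1.916, a one-sided p of 0.0277, which rounds to 0.028.
- n per arm = 2 × ((1.916 + 1.282)/0.5)² = 81.8, so 82. Three arms give 246, and 246 × 1.1 = 270.6, about the stated 270.
- The two-sided version does not reproduce: c = 2.212, threshold 0.0270, 98 per arm, 294 × 1.1 = 323.

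The stated figures are therefore a one-sided, two-dose, one-response design.

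**2. Any one success supports a claim, each test at the Dunnett threshold.** For independent subtests, 1 − 0.95³ = 0.143; the upper bound is 3 × 0.05 = 0.15. Simulation (2,000,000 draws, no true effect anywhere):

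| r | familywise error, one-sided | familywise error, two-sided Dunnett |
|---|---|---|
| 0 | 0.142 | 0.142 |
| 0.3 | 0.132 | 0.137 |
| 0.5 | 0.121 | 0.127 |
| 0.7 | 0.105 | 0.112 |
| 0.9 | 0.081 | 0.086 |
| 1 | 0.050 | 0.050 |

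Only perfectly correlated subtests return 0.05.

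**3. All three must succeed for a dose.** Each dose must pass every subtest at the Dunnett threshold, so familywise error stays within 0.05. Evaluable per arm: 90 × 0.9 = 81. Expected statistic: 0.5 × √(81/2) = 3.182. Power on one subtest: Φ(3.182 − 1.916) = 0.897. Power on all three, with effect 0.5 on each: 0.722 (r = 0), 0.752 (0.3), 0.776 (0.5), 0.806 (0.7).

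**4. Fixed order within each dose at alpha/2 = 0.025.** First-subtest power at 81 per arm:
- one-sided: Φ(3.182 − 1.960) = 0.889, against 0.897 at the Dunnett threshold;
- two-sided: Φ(3.182 − 2.241) = 0.827, against Φ(3.182 − 2.212) = 0.834 at the two-sided Dunnett threshold.

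**5. Holm over six tests, first step 0.05/6 = 0.0083.**
- one-sided: Φ(3.182 − 2.394) = 0.785;
- two-sided: Φ(3.182 − 2.638) = 0.707.

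**The case against.** The strongest reply is that the bullets in Section 12 are introduced as the basis of the power calculation, and that how three subtests combine is ordinary SAP content. Section 12 promises pre-specified primary analyses and an SAP fixed before unblinding. Part of this stands: the SAP is not shown and may contain a rule. But the protocol goes beyond leaving the matter open. It fixes a maximum error rate, a threshold and a power that do not cover its own list of primary variables. An SAP that corrects across subtests would have to depart from 0.028, or say to which subtest the 0.9 applies.

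Four stronger readings are tempting and are not supported:

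- **That the protocol directs each subtest to be tested at 0.028, so that the true error is 0.10 to 0.14.** The threshold is tied to the correction across doses. Nothing says it applies to each subtest or that one success suffices. The inflation is conditional on that rule and on r.
- **That error 0.05 and power 0.9 cannot both hold.** A single combined TAP response would match the design inputs and could keep both, if the 0.5 effect applies to it. A fixed order nearly keeps both for the first subtest.
- **That Day 180 multiplies the problem further.** Section 12 does name Days 90 and 180 as primary, while Section 3.1 names Day 90 only. That conflict must be reconciled separately, and a range for twelve tests would rest on a between-visit correlation the protocol does not give.
- **That the two alertness conditions and two concurrent tasks are extra primary tests.** Section 8 describes tasks, not endpoints. The count of six assumes one score per subtest.

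**Conclusion.** The point holds in conditional form. The stated 0.05, 0.028 and 0.9 are right for two doses on one response tested one-sided, and they do not extend to three primary subtests without a rule that the protocol lacks.

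Under an any-success rule, familywise error at Day 90 is roughly two to three times the stated maximum for r between 0 and 0.7, and still above it at 0.9. Under an all-three rule, error is controlled and the shortfall lies in the chance of a positive conclusion, which rests on the assumed effect of 0.5 on every subtest and 10% dropout. The marginal 0.9 in Section 12 is power per dose comparison, so the joint figure does not contradict it; it shows what the 0.9 does not promise.

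The sidedness is inferred from the reproduction, not stated. It hardly alters the inflation, but it does alter the power.

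**What to change.** Revise Section 12 before unblinding, as follows.

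1. Name one score for each of the three subtests and a fixed order of the subtests at Day 90.
2. Test each dose against placebo as its own chain at alpha/2 = 0.025, in that order, stopping the chain at the first non-significant subtest. Fixed order holds each chain at 0.025, and the two chains sum to at most 0.05 over all six tests.
3. Replace the 0.028 with this rule, and state that the planned power applies to the first subtest only.
4. State whether tests are one-sided or two-sided, and give the power on that basis.

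The cost is one paragraph and no patients. First-subtest power falls by less than one percentage point on either basis: to about 0.89 one-sided or about 0.83 two-sided. The two-sided figure is below 0.9 mainly because the sample size was set one-sided.

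If no order can be agreed, use Holm over the six tests and restate power: at the first step it is about 0.78 one-sided and 0.71 two-sided. Keeping the three subtests co-equal with marginal power 0.9 would need more participants. For example, one-sided Dunnett at 0.05/3 per subtest has threshold 0.0089 and needs 107 per arm before dropout, or 119 after (107/0.9).

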1. PROTOCOL SUMMARY / SYNOPSIS

Coordinator	FSNN – Foundation for the Study of Nanoneurosciences and Neuroregeneration
Title	The impact of N-PEP-12 dietary supplementation on attentional performance, cognition, and mental wellbeing of middle-aged and older healthy adults with subjective cognitive function complaints
Study Code	N-HANCE
Study Locations	Single-center
Dietary Supplement	MemoProve/Cebrium
Name of Active Substance	N-PEP-12
Indication	Middle and older age healthy adults
Study Design	Randomized, placebo-controlled, double-blind
Study Duration	Study start: 10/2022 Study end: 06/2024
Sample Size Calculation	
 • K=2 experimental treatments will be included in the trial. • A significance level of $\alpha=0.05$ will be used, in combination with Dunnett's correction. • The standard deviations of the responses will be assumed to be: $(\sigma_0, \dots, \sigma_K)=(1,1,1)$. • The minimum marginal power will be controlled to level $1-\beta=0.9$ under each of their respective least favourable configurations. • The interesting and uninteresting treatment effects will be: $\delta_i=0.5$ and $\delta_0=0$ respectively. • The target allocation to each of the experimental arms will be: the same as the control arm. • Therefore, the realised allocation ratios to the experimental arms are: $(r_1, \dots, r_K)=(1,1)$. • The maximum familywise error-rate is: 0.05. • The minimum marginal power is: 0.9. • The following critical threshold should be used with the chosen multiple comparison correction: 0.028. • 10% adjustment for dropouts 
The total required sample size is: $N=270$. The required sample size in each arm is: $(n_0, \dots, n_K)=(90,90,90)$.
 
Source: Grayling MJ, Wason JMS (2020) A web application for the design of multi-arm clinical trials. BMC Cancer 20:80. DOI: 10.1186/s12885-020-6525-0

Randomization	1:1:1 ratio, 3 blocks, ICH E9

Protocol Number: FSNANO08032022 -2.0 amendment 1 Date: 20032023	
STUDY Code: N-HANCE	Page 6 of 26

CRF	Electronic, open-source, self-developed, ICH E6
Primary Objectives	To assess the efficacy of N-PEP-12 on the Test of Attentional Performance outcomes in healthy middle-aged and older adults at 90 days after baseline.

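### Both doses are held to one single-step Dunnett threshold (0.028); step-down Dunnett would keep the same familywise 0.05 within a primary variable and raise power at no cost in participants

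*Protocol*

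**What the plan says.** The protocol's section 12 states that "K=2 experimental treatments will be included in the trial", each against the shared placebo arm. The synopsis says "A significance level of $\alpha=0.05$ will be used, in combination with Dunnett's correction", and section 12 repeats it. Section 12 then gives the error rate to be held, "The maximum familywise error-rate is: 0.05", the power criterion, "The minimum marginal power is: 0.9", and one cut-off for both comparisons: "The following critical threshold should be used with the chosen multiple comparison correction: 0.028".

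The planning values are an effect of 0.5 with SD 1 in every arm, equal allocation, a 10% dropout adjustment and 90 per arm (270 in total). Neither place mentions a step-down, closed or hierarchical procedure, gives the power to confirm both doses, or says whether the tests are one- or two-sided.

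**The concern.** Two null hypotheses are tested, one per dose. Once one has been rejected, only one is left, and by the closed testing principle it can be tested at the full 0.05 without raising the familywise error above 0.05. A single cut-off of 0.028 holds the second dose to a stricter standard than the stated error rate needs.

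Suppose 90 mg gives p = 0.001 and 45 mg gives p = 0.04. Under the present text 45 mg is not significant, although the trial's own familywise 0.05 would allow the claim. The loss always falls on the dose with the weaker result. Section 4 makes the two doses separate study groups, each tested against placebo, so each is a question of its own.

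**Working it through.** **Inputs (section 12, synopsis).** Two doses against one placebo arm, ratio 1:1:1, so the two test statistics have correlation 0.5; familywise error 0.05; marginal power 0.9; effect 0.5; SD 1; 10% dropout. All figures use the normal approximation and one primary variable at one time point. Φ2 is the bivariate normal distribution function with correlation 0.5.

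**1. Reproduce the plan's figures.**
- One-sided: solving 1 − Φ2(c, c) = 0.05 gives c = 1.9163, p = 0.0277, which rounds to the stated 0.028.
- n per arm = 2 × ((1.9163 + 1.2816) / 0.5)² = 81.8, so 82. The unrounded total is 245.4, and 245.4 × 1.1 = 270.0, the stated N.
- Two-sided: c = 2.2121, p = 0.0270, n = 97.6, so 98 per arm (294 before dropout). This matches neither 0.028 nor 270.

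The plan's numbers are therefore those of one-sided, single-step Dunnett.

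**2. Single-step power at 82 per arm, both effects 0.5.** Each statistic has mean θ = 0.5 × √(82/2) = 3.2016.
- Per dose: Φ(3.2016 − 1.9163) = Φ(1.2852) = 0.901.
- Both doses: Φ2(1.2852, 1.2852) = 0.833.
- At least one dose: 1 − Φ2(−1.2852, −1.2852) = 0.968.

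**3. Step-down power, same data.** The larger statistic must exceed 1.9163; if it does, the smaller must exceed 1.6449.
- Both doses: P(both > 1.6449) − P(both between 1.6449 and 1.9163) = 0.8961 − 0.0035 = 0.893.
- Per dose: 0.9006 + P(this statistic between the two limits and the other above 1.9163) = 0.9006 + 0.0296 = 0.930.
- At least one dose: 0.968, unchanged, because the first step is the same.

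**4. Other settings.**

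| Setting | Quantity | Single-step | Step-down |
|---|---|---|---|
| One-sided, 82 per arm | both doses | 0.833 | 0.893 |
| One-sided, 90 per arm | both doses | 0.871 | 0.920 |
| Two-sided, 82 per arm | both doses | 0.742 | 0.816 |
| Two-sided, 82 per arm | per dose | 0.839 | 0.876 |

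If only one dose works, its power stays at 0.901. Single-step testing would need about 96 evaluable per arm (0.894) to match the 0.893, which is 96 − 82 = 14 more per arm, or 42 in all.

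**5. Error control within one variable.** Simulated step-down familywise error (3 million draws) is 0.0497 under the global null. With one null dose, the false-positive rate on that dose is 0.044 when the other dose has an effect of 0.25 SD, 0.0495 at 0.5 SD, and 0.0497 for larger effects.

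**6. The rounded cut-off.** Used literally, 0.028 gives a familywise error of 0.0506 one-sided and 0.0519 two-sided.

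**7. Three uncorrected TAP subtests.** Simulated at 82 per arm, one-sided, with one dose effective at 0.5 SD on all three subtests and the other null on all three. The subtest correlations are assumed. The table gives the chance of at least one false claim for the null dose, and for comparison the chance of any false claim when neither dose works.

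| Correlation between subtests | Single-step | Step-down | Neither dose works (either rule) |
|---|---|---|---|
| 0 | 0.080 | 0.142 | 0.143 |
| 0.5 | 0.069 | 0.118 | 0.120 |

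**The case against.** Single-step Dunnett is a legitimate choice and delivers exactly what the protocol promises: familywise 0.05 and marginal power 0.9. The power to confirm both doses is a criterion the protocol never adopts, and its primary objective does not require both doses to succeed. The chance of at least one success does not change. Section 12 also imputes some missing outcomes, so the analysed number may be nearer 90 per arm, where the both-dose gain is about 0.05 rather than 0.06. All of this stands, and it makes the point an improvement rather than a correction.

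It can also be said that 0.028 is only a planning value, since it sits in a list introduced as the basis for power and the analysis is left to a SAP. That weakens the point but does not remove it: the sentence prescribes the threshold to be used.

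The weightiest objection concerns the subtests. With three primary TAP subtests and no stated correction across them, the stricter second step gives some incidental protection against false claims for an ineffective dose beside an effective one. Step-down gives that up (0.07–0.08 becomes 0.12–0.14), although it does not exceed the error already present when neither dose works. This stands and shapes the fix.

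A reader might infer that the threshold is wrong or the trial underpowered. The documents do not support that: the stated figures reproduce and the 0.9 is met. A reader might also infer that step-down is free of any error cost across the whole trial. That holds only within one primary variable.

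**Conclusion.** A cheap improvement, not an error. At the same familywise 0.05 per primary variable, step-down Dunnett rejects everything the single-step rule rejects and sometimes more. Per-dose power rises from 0.90 to 0.93 and both-dose power from 0.83 to 0.89; a dose that works alone gains practically nothing.

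These sizes rest on one variable at one time point, 82 evaluable per arm, both true effects at 0.5 SD, and the one-sided reading that the protocol's own numbers imply but its text does not state. The direction of the gain does not depend on the sidedness or on whether 82 or 90 per arm are analysed.

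**What to change.** In the synopsis and section 12, replace the single threshold by a rule such as:

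> Step-down Dunnett within each primary variable. The smaller of the two dose p-values is compared with the exact Dunnett critical level for familywise 0.05 (0.0277 one-sided, 0.0270 two-sided). If it is significant, the other dose is tested at 0.05 with the same sidedness. Otherwise testing stops.

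State the sidedness, and use the exact level rather than 0.028. Settle first how alpha is divided over the three TAP subtests and the primary time point (90 days in section 3.1; 90 and 180 days in section 12), and nest the rule inside that allotment, recomputing both levels if the allotment is below 0.05. Keep the ordinary Dunnett simultaneous intervals for estimation. The stated marginal power of 0.9 remains correct as a minimum.

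**Cost.** No participants and no data. The text change is short, but section 15.4 requires a signed amendment with prior ethics committee review, and the rule must be fixed before unblinding. The second dose may be declared effective while its single-step simultaneous interval includes zero, so the report must say that the decision is step-down. Until the subtests are corrected for, the higher chance of a false claim for an ineffective dose has to be accepted openly.
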